Enrollment of 3 subjects at the target RP2D (1500 mg/m² Q2W) will begin once the 1000 mg/m² Q2W dose level has been deemed tolerable. A de-escalation dose cohort will be opened at 1250 mg/m² Q2W if 1500 mg/m² Q2W has been deemed not tolerable. Subjects enrolled in the 1000 mg/m² Q2W dose level will continue treatment at that dose level (unless they meet study treatment discontinuation criteria) and will be dose escalated to the RP2D after the RP2D is deemed tolerable.

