5.3.1.6 Other

- 12-lead electrocardiogram (ECG)
- ECOG performance scores
- Body Mass Index (BMI)

$$\text{BMI} = \text{weight (kg)} / [\text{height (m)}]^2$$

- Duration of exposure

Duration of exposure to a study drug will be calculated in days, using the following formula:

(Date of last dose of study drug – Date of first dose) + 1

When the start or stop date is missing, for example if the subject is ongoing, then the exposure will be treated as missing.

- Cumulative Actual Dose

Total amount of study drug actually taken by the patient from first dose date to last dose date

- Planned Dose Intensity

Planned dose intensity for ASP1650 is 1000 mg/m² Q2W or 1500 mg/m² Q2W.

- Actual Dose Intensity

Defined as the cumulative actual dose in mg divided by duration of exposure in days.

- Relative Dose Intensity (RDI)

Actual Dose Intensity

----- x 100

Planned Dose Intensity

- Previous and concomitant medication

- Previous medication is defined as medication with at least one dose taken before the date of the first dose of study drug.
- Concomitant medication is defined as medication with at least one dose taken between the date of first dose (inclusive) and the date of last dose (inclusive) of study drug.

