6.3 Study Drug

Summaries of drug exposure and relative dose intensity (RDI) by dose level and overall will be presented using each subject's assigned dose at treatment start.

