6.3.1 Exposure

Summary statistics (n, mean, standard deviation, median, minimum and maximum) will be presented for the following continuous variables:

- Duration of exposure
- Total (mg) ASP1650 used per subject
- Average dose (mg/m² Q2W) per subject

As a categorical variable: number and percentage of subjects in each of the following duration categories:

- Number of dose delay, dose reduction, dose discontinuation, dose interruption
- Number of cycles initiated/completed

Reasons for dose delay, reduction, discontinuation or interruption will be presented in a listing.

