6.3.2 Relative Dose Intensity

RDI will be summarized by dose level and overall for subjects in the SAF whose total study drug infused and first and last days of treatment are known. RDI will be presented in two ways:

- As a continuous variable, summary statistics will be presented.
- As a categorical variable, RDI will be summarized using the following categories:
 - <50
 - 50 – < 75
 - 75 – < 90
 - 90 – <= 100
 - > 100
 - Unknown

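### The SAP's relative dose intensity formula mixes units and drops 13 of the last cycle's 14 days, so a fully dosed, on-time subject cannot score 100%

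*SAP*

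**What the plan says.** SAP 5.3.1.6 defines the pieces of RDI in sequence.

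- Duration of exposure: "Date of last dose of study drug – Date of first dose) + 1", in days.
- Cumulative dose: the total amount of drug given.
- Actual dose intensity: "Defined as the cumulative actual dose in mg divided by duration of exposure in days".
- Planned dose intensity: "Planned dose intensity for ASP1650 is 1000 mg/m² Q2W or 1500 mg/m² Q2W".
- RDI: actual over planned, times 100.

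SAP 6.3.2 reports RDI as a continuous variable and in bands: "RDI will be summarized using the following categories", namely below 50, 50 to under 75, 75 to under 90, 90 to 100, above 100, and unknown. SAP 6.3 presents exposure and RDI by dose level using each subject's "assigned dose at treatment start".

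Two design features bear on the denominator, both in SAP 2.2. One is a conditional cohort: "A de-escalation dose cohort will be opened at 1250 mg/m² Q2W if 1500 mg/m² Q2W has been deemed not tolerable". The other is that subjects who start at 1000 mg/m² "will be dose escalated to the RP2D after the RP2D is deemed tolerable".

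**The concern.** A fully compliant subject should have an RDI of 100%. Three features of the definition stand in the way.

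1. **Units.** The numerator is in mg per day and the denominator in mg/m² per 2 weeks. Neither SAP 5.3.1.6 nor SAP 6.3.2 supplies a conversion.
2. **Time at risk.** Each dose covers a 14-day cycle, but the duration ends on the day of the last dose. That dose is counted in full while only 1 of its 14 days is.
3. **Planned dose.** There is no planned value for the 1250 mg/m² cohort, and no explicit denominator for subjects whose planned dose changes during treatment.

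At stake is a table meant to show how much of the intended dose was delivered at each dose level. For 2 or more doses the first two errors act in opposite directions, so repairing only the units turns a falsely low table into a falsely high one. The inflation is greatest in subjects who stop early.

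**Working it through.** **Inputs.** The dosing interval is 14 days, with at most 12 cycles (Protocol 5.1.1). The duration and intensity definitions are from SAP 5.3.1.6 and the bands from SAP 6.3.2. The documents give no BSA value; I assume 1.9 m², range 1.6 to 2.3. They state no RDI figure to reproduce, so the benchmark is k full doses exactly 14 days apart, which should give 100%.

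**Duration.** For k on-schedule doses the SAP gives 14(k − 1) + 1 = 14k − 13 days, against 14k days of planned treatment.

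**Literal formula.** With dose level D in mg/m², RDI = 100 × [k × D × BSA / (14k − 13)] / D = 100 × k × BSA / (14k − 13). D cancels, so the result is the same at every dose level.

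**Units aligned, SAP duration kept.** RDI = 100 × [k × D / (14k − 13)] / (D/14) = 100 × 14k / (14k − 13).

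| Full on-time doses | SAP duration (days) | Literal, BSA 1.9 | Units aligned |
|---|---|---|---|
| 1 | 1 | 1.9/1 = 190% | 14/1 = 1400% |
| 2 | 15 | 3.8/15 = 25.3% | 28/15 = 186.7% |
| 4 | 43 | 7.6/43 = 17.7% | 56/43 = 130.2% |
| 6 | 71 | 11.4/71 = 16.1% | 84/71 = 118.3% |
| 12 | 155 | 22.8/155 = 14.7% | 168/155 = 108.4% |

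Over the assumed BSA range, the literal result for 2 to 12 doses runs from 12 × 1.6/155 = 12.4% to 2 × 2.3/15 = 30.7%. One dose gives 160% to 230%. The bands do not depend on the BSA assumption: to reach 50% at 2 doses, BSA would have to be 0.5 × 15/2 = 3.75 m², and more doses would need a larger value still.

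**Reduced or delayed subjects, units aligned.** The planned dose is 1500 mg/m², or 1500/14 = 107.14 mg/m² per day. The reference value counts the last dose's full 14 days.

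| Pattern | SAP duration | Reference |
|---|---|---|
| 1500, then 1250 three times | (5250/43)/107.14 = 114.0% (above 100) | 5250/6000 = 87.5% (75 to under 90) |
| 12 cycles, 1250 from cycle 2 | (15250/155)/107.14 = 91.8% (90 to 100) | 15250/18000 = 84.7% (75 to under 90) |
| 12 cycles, 1000 from cycle 2 | (12500/155)/107.14 = 75.3% (75 to under 90) | 12500/18000 = 69.4% (50 to under 75) |
| 4 full doses, 13 days total delay | 56/(43 + 13) = 100.0% (90 to 100) | 56/69 = 81.2% (75 to under 90) |

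**Denominator gaps, duration corrected.** A cohort 1 subject given 5 cycles at 1000 and 7 at 1500, exactly as planned, scores (5 × 1000 + 7 × 1500)/(12 × 1000) = 15500/12000 = 129.2% against the starting dose. A fully dosed 1250 mg/m² subject scores 1250/1500 = 83.3% or 1250/1000 = 125%, depending on which listed value is borrowed.

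**The case against.** The strongest reply is that nobody would publish an RDI of 15% for a fully dosed subject, so a programmer would convert the units. SAP 6.3.1 also plans an average dose per subject in mg/m² Q2W, which shows the intended scale. That makes the literal outcome less likely, but the average dose is not linked to RDI. SAP 6.1 refers to separate table specifications, which I have not seen, but it describes them as covering formats. A unit conversion alone would also leave the duration error untouched.

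The plus-1 formula is a usual definition of exposure duration. It can stay for that summary; the problem is reusing it as the RDI time base.

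SAP 6.3 might be read as fixing the denominator at the starting dose. It reads more naturally as a rule for grouping subjects in the table. On the other reading, a subject escalated as planned would be reported as over-dosed. The 1250 mg/m² gap matters only if that cohort opens.

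Two points stand. The 13-day delay example averages 13/3 = 4.3 days per interval, which can fall within the +5 day window in Protocol 5.1.2.2. It shows lost intensity, not necessarily a departure from schedule. Also, RDI is not a protocol endpoint, and SAP 6.3.1 separately tabulates "Number of dose delay, dose reduction, dose discontinuation, dose interruption" and lists the reasons, so reductions and delays would remain visible elsewhere.

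**Conclusion.** The concern holds: the definition is wrong as written, not merely short of detail. For full on-time dosing of 2 to 12 doses it gives about 12% to 31% read literally (BSA assumed 1.6 to 2.3 m²), or 108% to 187% with units aligned. Which wrong table appears depends on an unwritten programming choice, but neither reading returns 100%. The units-aligned figures need no BSA assumption. They rest on each dose covering its 14-day cycle, which follows from the dosing schedule, although the documents state no RDI benchmark.

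The consequence is confined to a descriptive exposure table. RDI drives no decision rule, and neither the RP2D determination nor the Simon two-stage assessment of response is affected. The definition should be corrected before database lock, but the trial's conclusions do not hang on it.

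**What to change.** For RDI only, restate the derivation in SAP 5.3.1.6:

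- RDI duration = last dose date − first dose date + 14 days. Leave the existing duration of exposure as it is.
- Actual intensity = cumulative mg/m² (each dose in mg divided by the BSA used for that dose) / (RDI duration/14).
- Planned intensity = mean protocol-planned mg/m² per 14-day cycle over the cycles given. Use the planned dose at each cycle for cohort 1 subjects who are escalated, leave it unreduced after reductions for adverse events, and list 1250 mg/m² in case that cohort opens.
- RDI = 100 × actual/planned.

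For k full on-time doses the duration is 14(k − 1) + 14 = 14k days, so RDI is 100% for every k from 1 to 12, including planned escalation. This is an analysis convention and changes no dosing rule.

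The cost is SAP wording and programming, plus recording the cycle at which planned escalation applies to each cohort 1 subject. Dose is already recorded every cycle (Protocol 5.1.4), and the average dose in mg/m² already planned in SAP 6.3.1 needs the same per-m² data. The sponsor should confirm that the BSA actually used for dosing can be recovered, since Protocol 5.1.2.1 has it recalculated only after a weight change of at least 10%.

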5.4 Major Protocol Deviations and Other Analyses

Protocol deviations as defined in the study protocol (Section 8.3 Protocol Deviations) will be assessed for all subjects registered. The number and percentage of subjects meeting any criteria will be summarized for each criterion and overall, by cohort and dose level and overall as well as by study site. Subjects deviating from a criterion more than once will be counted once for the corresponding criterion. Any subjects who have more than one protocol deviation will be counted once in the overall summary. A data listing will be provided by site and subject.

The protocol deviation criteria will be uniquely identified in the summary table and listing. The unique identifiers will be as follows:

PD1 - Entered into the study even though they did not satisfy entry criteria,

PD2 - Developed withdrawal criteria during the study and was not withdrawn,

PD3 - Received wrong treatment or incorrect dose,

PD4 - Received excluded concomitant treatment.

6 STATISTICAL METHODOLOGY

6.1 General Considerations

Continuous data will be summarized descriptively including the number of subjects (n), mean, standard deviation, median, minimum and maximum. Categorical data will be summarized by frequencies and percentages. Percentages by categories will be based on the number of subjects with no missing data, i.e. the percentages for the non-missing categories will add up to 100%.

All data summarization and analyses will be performed using SAS® Version 9.4 or higher on Linux. Specifications for table, figures, and data listing formats can be found in the TLF specifications.

6.2 Study Population

6.2.1 Disposition of Subjects

The number and percentage of subjects who completed and discontinued treatment and reasons for treatment discontinuation will be presented for all FAS subjects and for subjects in the SAF by dose level and overall. For the discontinuation, the primary reason reported by the investigator will be summarized. Similar tables for screening disposition, as well as both 30-day and long term follow-up disposition will also be presented. All disposition details and dates of first and last evaluations for each subject will be listed.

6.2.2 Protocol Deviations

The number and percentage of subjects with the following protocol deviation criteria will be summarized for each criterion and overall, by treatment group and total as well as by investigative site. Subjects deviating from a criterion more than once will be counted once for the corresponding criterion.

The unique identifiers will be as follows:

- PD1 - Entered into the study even though they did not satisfy entry criteria,
- PD2 - Developed withdrawal criteria during the study and was not withdrawn,
- PD3 - Received wrong treatment or incorrect dose,
- PD4 - Received excluded concomitant treatment.

6.2.3 Demographic and Other Baseline Characteristics

Demographics and baseline characteristics including age, sex, race, ethnicity, height, weight, baseline BMI and BSA, time in days from diagnosis to registration, tumor location, tumor type, number of prior lines of medication therapy, presence of visceral metastases, late relapse, and prior high dose chemotherapy will be summarized by dose level and overall for FAS and SAF.

TNM staging will also be listed for the SAF.

6.2.3.1 Medical History

Medical history will be coded by MedDRA and listed and summarized by SOC and PT, by cohort and dose level and overall for the SAF.

6.2.3.2 Substance Use

History of substance use, including use of alcohol, tobacco, or drugs will be listed for the SAF.

6.2.3.3 Prior Procedures

Prior Procedures, Prior Therapy including best response, and Prior Radiation for cancer will be listed and summarized by dose level and overall for the SAF.

6.2.3.4 Liver Abnormality

Liver abnormalities will be listed for the SAF.

6.2.4 Previous and Concomitant Medications

Previous and concomitant medications will be summarized by preferred WHO name by dose level group for the SAF. Subjects taking the same medication multiple times will be counted once per medication and investigational period. Previous medications are defined as medications that patients started and ended prior to first administration of study medication. Concomitant medications are defined as any medications that patients took after the first dose of study medication and through 90 days from last dose of study drug. Medications that started prior to first administration of study drug and continued while study drug was given will be counted in both previous and concomitant medications.

Previous and concomitant medications will be listed.

6.2.4.1 Prior Radiation Therapy

Frequency tabulations of subjects with prior radiation therapy will be presented for SAF.

6.2.4.2 Prior Procedures for Tumors

Frequency tabulations of subjects with prior procedures for tumors will be presented for SAF.

6.2.4.3 Prior Cancer Therapy

Summary of prior cancer therapy will be presented for SAF.

6.2.4.4 Disease History

Summary of disease history will be presented for SAF.

6.2.4.5 New Anti-Cancer Therapy

Summary of new anti-cancer therapy will be presented for SAF.

6.3 Study Drug

Summaries of drug exposure and relative dose intensity (RDI) by dose level and overall will be presented using each subject's assigned dose at treatment start.

6.3.1 Exposure

Summary statistics (n, mean, standard deviation, median, minimum and maximum) will be presented for the following continuous variables:

- Duration of exposure
- Total (mg) ASP1650 used per subject
- Average dose (mg/m² Q2W) per subject

As a categorical variable: number and percentage of subjects in each of the following duration categories:

- Number of dose delay, dose reduction, dose discontinuation, dose interruption
- Number of cycles initiated/completed

Reasons for dose delay, reduction, discontinuation or interruption will be presented in a listing.

6.3.2 Relative Dose Intensity

RDI will be summarized by dose level and overall for subjects in the SAF whose total study drug infused and first and last days of treatment are known. RDI will be presented in two ways:

- As a continuous variable, summary statistics will be presented.
- As a categorical variable, RDI will be summarized using the following categories:
 - <50
 - 50 – < 75
 - 75 – < 90
 - 90 – <= 100
 - > 100
 - Unknown

6.4 Analysis of Efficacy

6.4.1 Analysis of Primary Efficacy Endpoint

Efficacy analyses will be conducted on the FAS.

6.4.1.1 Best Overall Response

Best Overall Response both with and without subsequent confirmation will be presented for the Full Analysis Set.

Best percentage change from baseline in the size of the target lesions will be presented in a waterfall plot. A swimmer plot will display study events by participant.

6.4.1.2 Objective Response Rate

ORR is defined as the proportion of subjects for each dose level whose best overall response is rated as confirmed CR or PR by modified RECIST 1.1. ORR by dose level will be calculated and its 90% confidence interval will be constructed by Clopper-Pearson method.

6.4.1.3 Sensitivity Analysis for Primary Efficacy Endpoint

ORR as assessed by RECIST 1.1 alone and by serum markers alone will be calculated by dose level and its 90% confidence interval will be constructed by Clopper-Pearson method.

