 - An increase in AFP or β hCG ($\geq 50\%$ increase in 2 separate samples collected at least 1 week apart are required if rising tumor markers are the only evidence of failure).

NOTE: Subjects with clinically growing teratoma (enlarging mature teratoma arising during or after chemotherapy for a non-seminomatous germ-cell tumor and with normal serum levels of AFP and β hCG) should undergo surgical resection if feasible.

10. Subjects with late relapse (> 2 years) not amenable to resection are eligible.
11. Subjects must have evidence of recurrent or metastatic carcinoma by 1 or more of the following:
- Subject has measurable disease according to RECIST v1.1 within 28 days prior to the first dose of study treatment. For subjects with only 1 measurable lesion and prior radiotherapy, the lesion must be outside the field of prior radiotherapy or must have documented progression following radiation therapy.
 - Subject has a baseline rising tumor marker (AFP or β hCG).

NOTE: If a rising tumor marker is the only evidence of PD, at least 2 consecutive rising values at least 1 week apart are needed. Subjects with only evidence of disease as rising tumor marker AFP and β hCG will be assessed for alternate causes of increased serum levels of these markers, such as cross reaction with luteinizing hormone (LH) (can be tested if needed by testosterone suppression of LH), hepatitis, use of marijuana or second primary tumor.

Physical or Laboratory Findings:

12. Subject must have an available tumor specimen in a tissue block or unstained serial slides, or subject is an appropriate candidate for tumor biopsy as determined by the investigator and is amenable to undergoing a tumor biopsy during the screening period.
13. Subject has ECOG performance status of 0 to 2.

14. Subject must meet all of the following criteria based on the centrally analyzed laboratory tests within 14 days prior to the first dose of study treatment. If repeat screening labs are required, local laboratory results can be used to confirm eligibility. In case of multiple central laboratory data within this period, the most recent data should be used to determine eligibility.
- Hemoglobin ≥ 8 g/dL
 - Absolute neutrophil count $\geq 1.0 \times 10^9/L$
 - Platelets $\geq 75 \times 10^9/L$
 - Albumin ≥ 2.5 g/dL
 - Total bilirubin $\leq 2 \times$ ULN or direct bilirubin \leq ULN for subjects with total bilirubin levels $> 2 \times$ ULN

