5.3 Efficacy and Immunogenicity Assessments

5.3.1 Efficacy Assessments

Disease response and progression will be evaluated in this study using modified RECIST v1.1, incorporating RECIST v1.1 and serum tumor biomarker response criteria. In addition, response assessment using RECIST v1.1 alone for subjects with measurable disease at baseline and serum tumor biomarker response criteria alone for subjects with elevated serum tumor markers ($> 2 \times$ ULN AFP or $> 2 \times$ ULN β hCG) at baseline will be performed as sensitivity analyses.

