5.3.1.3 Response Criteria Based on Serum Tumor Biomarkers

Blood will be drawn for the measurement of serum AFP and serum β hCG at day 1 of every cycle and during the post treatment period follow up period to align with imaging assessment (every 6 weeks + 7 days counting from C1D1 for the first 24 weeks and then every 12 weeks ± 7 days thereafter) until the subject develops radiological disease progression per RECIST v1.1 by local investigator evaluation or starts other systemic anticancer treatment. To evaluate the effect of ASP1650 on changes in serum β hCG and AFP, disease response will be derived for subjects with elevated serum tumor markers ($> 2 \times$ ULN AFP or $> 2 \times$ ULN β hCG) at baseline using the following definition:

- CR is defined as values that fall below the ULN for the assay employed. Confirmed CR must remain at that level for at least 4 weeks.
- PR is defined by serum tumor markers (AFP and β hCG) that are decreasing. Elevated serum tumor markers (AFP or β hCG) values must fall $\geq 90\%$ below baseline pretreatment levels for β hCG or 50% decrease below baseline pretreatment levels for AFP. PR must persist for at least 6 weeks to be a confirmed PR. If both tumor markers are elevated and 1 falls below 90%, the other should fall at least below 50% of baseline pretreatment levels.
- Stable disease (SD) is defined as no change or a change in serum tumor biomarkers that does not qualify as CR, PR or PD. Durable SD is defined as SD that is maintained for at least 12 weeks.
- PD is defined as $\geq 50\%$ increase in AFP or β hCG in 2 samples, 1 week apart compared to nadir.

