7.4 Analysis of Efficacy

Efficacy analysis will be conducted on the FAS and PPS. The interpretation of results from statistical tests will be based on the FAS. The PPS will be used to assess the robustness of the results from the statistical tests based on the FAS. Response assessment will be based on modified RECIST v1.1, RECIST v1.1 alone and serum marker alone.

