5.2.3 Progression-Free Survival (PFS)

PFS is defined as the time from the date of first dose until the date of disease progression as assessed by modified RECIST 1.1, or until death due to any cause. If a subject has neither progressed nor died, the subject will be censored at the date of last disease assessment or at the date of registration if no post-baseline radiological assessment is available. Subjects who receive any further anticancer therapy for the disease before disease progression will be censored at the date of the last disease assessment before the anticancer therapy started. If progression or death occurs after missing 2 scheduled disease assessments, the subject will be censored at the date of last disease assessment or at the date of registration if no post-baseline disease assessment is available. A subject has missed 2 scheduled disease assessments if the gap between two disease assessments is more than 2.5 times the scheduled disease assessment interval. During treatment, this will be 105 days (2.5 x 42 days during treatment for the first 24 weeks); during the follow-up period this will be 210 days (2.5 x 84 days during follow-up).

PFS (in days) is calculated as:

(Date of death, or Progression assessed by modified RECIST 1.1, or censoring) – (Date of first dose) +1.

To apply the cut-off date to PFS is to exclude disease assessments, death and anti-cancer therapy date after cut-off date in the analysis.

Note: Patient cannot be censored at “Not Evaluable (NE)”. If NE is the only previous assessment, then PFS will be censored at Day 1.

PFS will be calculated for each subject using RECIST 1.1 alone, and serum markers alone.

Table 3 PFS Definition

Situation	Date of Event or Censor	Outcome
No evaluable post-baseline efficacy assessments, no death	Date of first dose	Censor
Subject did not receive new anti-cancer therapy:		
Disease progression documented per modified RECIST v1.1	Date of PD	Event
No disease progression, but death recorded on eCRF	Date of death	Event
No PD nor death	Date of last efficacy assessment or at the date of first dose if no postbaseline efficacy assessment is available	Censor
Subject received new anti-cancer (ACT) therapy:		
Disease progression documented per modified RECIST v1.1 after new ACT	Date of last efficacy assessment before start of new anti-cancer therapy or at the date of first dose if no post-baseline efficacy assessment is available	Censor

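### For RECIST-alone and marker-alone ORR and CBR, the SAP omits the baseline limits in protocol 5.3.1 and leaves the FAS as the only denominator; the protocol's own statistics sections do the same

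*SAP*

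**What the plan says.** **Protocol 5.3.1** describes two sensitivity analyses, each with its own baseline condition. The imaging one is "response assessment using RECIST v1.1 alone for subjects with measurable disease at baseline". The other one, based on AFP and βhCG, is described as "serum tumor biomarker response criteria alone for subjects with elevated serum tumor markers", where elevated means AFP or βhCG above 2 x ULN at baseline. **Protocol 5.3.1.3** repeats the marker condition: "disease response will be derived for subjects with elevated serum tumor markers".

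**SAP 5.1.1 and 6.4.1.3** plan both ORR analyses without either condition: "ORR as assessed by RECIST 1.1 alone and by serum markers alone will be calculated by dose level". **SAP 5.2.1** adds CBR by RECIST alone and by markers alone, and **SAP 6.4.2.1** gives the CBR analysis; neither states a subset. **SAP 6.4.1** fixes the population: "Efficacy analyses will be conducted on the FAS". SAP 4.1 defines the FAS as everyone enrolled.

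**The protocol's statistics text** is equally general. Section 7.4 reads "Efficacy analysis will be conducted on the FAS and PPS" and goes on to list modified RECIST, RECIST alone and markers alone. Section 7.4.1.2 gives ORR by RECIST with no subset, and the synopsis puts all efficacy analyses on the FAS.

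**Eligibility.** Inclusion criterion 11 in protocol 3.2 reads "Subjects must have evidence of recurrent or metastatic carcinoma by 1 or more of the following". The two routes are measurable disease and a rising AFP or βhCG.

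**The concern.** A subject may enter on markers alone, or on measurable disease with normal markers. The first has no measured lesion that can shrink, and the second has no elevated marker that can fall. If both stay in the denominator of the criterion that cannot register a response in them, that ORR is diluted by an amount that depends on case mix and not on the drug.

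The two analyses should help a reader see whether a composite response rate is carried by imaging or by markers. Different, unstated fractions of non-assessable subjects in the two denominators make the two rates hard to compare. RECIST-alone ORR is also a named secondary endpoint (protocol 2.3.2), so its denominator will be read as a result in its own right.

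CBR has a further problem. Protocol 5.3.1.3 defines marker SD as no change, or any change short of CR, PR or PD. A subject whose markers stay normal for 12 weeks fits the wording of durable SD and could count as a marker-alone clinical benefit.

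**Working it through.** **1. The plan's own figure.** SAP 3 gives a Simon design: 13 subjects, stop at 1 or fewer responses; otherwise 34 in total, reject at 6 or more; null 10%, alternative 25%. The exact rejection probability is the sum over x = 2 to 13 of P(Bin(13, p) = x) times P(Bin(21, p) ≥ 6 − x).

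- p = 0.10: 0.0957, within the stated 10%.
- p = 0.25: 0.811, against the stated 80%.

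The design reproduces. It concerns ORR by modified RECIST, so the point made here does not touch it.

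**2. Which denominator the text gives.**

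| Analysis | Protocol 5.3.1 | Protocol synopsis, 7.4, 7.4.1.2 | SAP |
|---|---|---|---|
| RECIST-alone ORR | measurable disease at baseline | FAS, no subset | FAS by 6.4.1, no subset |
| Marker-alone ORR | AFP or βhCG > 2 x ULN at baseline | FAS, no subset (synopsis, 7.4) | FAS by 6.4.1, no subset |
| CBR by either criterion | response assessment limited as above | no subset | no subset |

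**3. Effect of the denominator on ORR.** With x responders, all of them assessable, the rate is x/34 on all subjects and x/n on the n assessable subjects. The ratio is 34/n. The 90% Clopper-Pearson limits are the 0.05 quantile of Beta(x, n − x + 1) and the 0.95 quantile of Beta(x + 1, n − x).

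Inputs: 34 is the full phase 2 size (SAP 3). The documents give neither the assessable share nor the responder count, so both are assumptions: x = 5, and a share of 50% to 100%.

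| Assumed share | n | ORR | 90% CI |
|---|---|---|---|
| 100% | 34 | 5/34 = 14.7% | 6.0 to 28.5 |
| 90% | 31 | 5/31 = 16.1% | 6.6 to 31.0 |
| 80% | 27 | 5/27 = 18.5% | 7.6 to 35.1 |
| 70% | 24 | 5/24 = 20.8% | 8.6 to 38.9 |
| 50% | 17 | 5/17 = 29.4% | 12.4 to 52.2 |

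With 6 responders the range is 6/34 = 17.6% (8.0 to 31.9) to 6/17 = 35.3% (16.6 to 58.0). The arithmetic is the same for either criterion; only the assessable share differs.

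**4. Direction for CBR.** In RECIST-alone CBR, marker-only subjects dilute the rate in the same way. In marker-alone CBR, a marker-normal subject cannot add a response but might add a durable SD, so the FAS version could be too low or too high. The documents do not allow a figure.

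**The case against.** **The SAP follows the protocol's statistics sections.** This is correct. A reader might infer that the SAP departs from a clear protocol rule, but the synopsis, 7.4 and 7.4.1.2 all use the FAS without a subset. The conflict lies inside the protocol as well, and a correction to the SAP alone would leave it standing.

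**The SAP nowhere says that non-assessable subjects count as failures.** Also correct. That reading follows from 4.1 and 6.4.1. SAP 6.1 bases category percentages on subjects without missing data, and protocol 5.3.1.3 derives marker response only for subjects with elevated markers, so a programmer could leave the others out. This softens the charge from a wrong denominator to an unsettled one, but two programmers could then report different rates from the same text.

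**Not everyone outside the subsets is unable to respond.** A subject between 1 and 2 x ULN can still fall below the ULN, which is the marker CR wording. The modified RECIST table also has a CR row with no target lesion. The dilution is exact only for subjects with no lesion to follow or with normal markers.

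**An all-enrolled denominator is conservative, not useless.** True. Responder counts by imaging and by markers can still be set against the composite on a common base, which is a reason to keep that version as supportive.

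**PFS.** SAP 5.2.3 says "PFS will be calculated for each subject using RECIST 1.1 alone, and serum markers alone", and a reader might infer that marker-alone PFS is biased upward because marker-normal subjects are censored. The documents do not support this. SAP 6.4.2.3 confines PFS to phase 2 subjects, and the conditions in protocol 5.3.1 are worded for response assessment. Marker PD is a rise of at least 50% from nadir with no ULN floor, so a marker-normal subject can progress, and death is an event. Neither direction nor size is established.

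**DOR.** A reader might extend the fix to DOR. It would do little there, because DOR already covers confirmed responders only.

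**Conclusion.** The point stands for ORR and CBR. The SAP omits the baseline conditions that protocol 5.3.1 attaches to the criterion-alone response analyses, and its only named efficacy population is all enrolled subjects. The protocol is inconsistent on the same matter. On the FAS reading both criterion-alone ORRs are diluted by a factor equal to the assessable share. With 5 responders among 34, an 80% share moves ORR from 14.7% to 18.5%, and a 50% share moves it to 29.4%; at 90% the change is small (16.1%).

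These figures rest on an assumed share and responder count, and on all responders lying inside the subset. The downward direction for marker-alone ORR also assumes that a marker that was normal throughout is not counted as having fallen below the ULN. The direction for marker-alone CBR is open. No claim is made about PFS bias. The primary ORR by modified RECIST, the stage I futility rule and the final decision rule are unaffected, so this should be fixed but does not threaten the main conclusion.

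**What to change.** In SAP 5.1.1, 5.2.1, 6.4.1.3 and 6.4.2.1:

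- Set the RECIST-alone ORR and CBR denominator to FAS subjects with measurable disease at baseline.
- Set the marker-alone ORR and CBR denominator to FAS subjects with AFP or βhCG above 2 x ULN at baseline.
- Report n for each subset, and the number in neither. Criterion 11 asks for a rising marker, not one above 2 x ULN, so a subject could fall outside both.
- Keep the all-FAS version as supportive, and state how non-assessable subjects count in it.

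In the protocol, reconcile 5.3.1 with the synopsis, 7.4 and 7.4.1.2. DOR needs no change. A subset version of marker-alone PFS is optional.

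The cost is wording and two flags derived from baseline imaging and AFP/βhCG results that are already collected. The downside is smaller denominators and wider intervals: at 17 rather than 34 subjects with 5 responders, the 90% interval widens from 22.5 points (28.5 − 6.0) to 39.8 points (52.2 − 12.4). The change should be made before database hard lock, so that in this open-label trial the denominator is not chosen with responses in view.
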